7.2 SAS code fragments for sensitivity analyses (FCS model) of the primary endpoint

The SAS code for MI imputation with FCS model is written as follows:

```

/* Model MI FCS */
Proc MI data= Main_analysis seed =xxx nimpute =100 out = logistic_ficout;
Var _trt centre _b_fibrinogen_ key_covariates_for_MI Resp;
class _trt centre _b_fibrinogen_ key_covariates_for_MI resp;
fcs logistic(resp = _trt centre _b_fibrinogen key_covariates_for_MI
/details) ;
run;
/* PRIMARY MODEL OF ANALYSIS */
proc logistic data = logistic_ficout descending;
class _trt centre _b_fibrinogen(PARAM=REF REF="> 4 g/L") / param=glm;
model _resp = _trt centre _b_fibrinogen /influence iplots;
ods output ParameterEstimates =_ logistic_parms ;
by _imputation_;
run;

```

```

/* COMBINE RESULTS OF MULTIPLE IMPUTATIONS, INFERENCES */
proc mianalyze parms (classvar =classval) = logistic_parms;
class _trt;
modeleffects _trt;
ods output parameterestimates= logistic_outcome;
run;
data res;
set logistic_outcome;
estimate_back=exp(estimate);
lcl_back= exp(estimate -1.96*stderr);
ucl_back= exp(estimate +1.96*stderr);
run;
proc print data= res;run;

```

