Handling missing data	12.7. General Rules for Handling of Missing or Inconsistent Data “Concerning the primary efficacy endpoint, missing data (including incomplete dates) will be estimated as failures.”	
SAP: “No imputation of missing data will be proposed for the primary analysis of the primary endpoint. “
 
Rationale for change: There is no best method for handling missing data. The approach for handling missing data as recommended by the EMA guideline on missing data in confirmatory trials (EMA, 2010) should consider various missingness mechanisms along with subsequent analyses.
 
Three methods for handling missing data will be considered.
 
 - The method n°1 considers no replacement of missing data (which is considered as the primary method). - The method n°2 replaces missing data by failures regardless of the randomized treatment (which is considered as a sensitivity method). This method relies on strong assumptions corresponding to a particular MNAR missingness mechanism, and should thus not be envisaged in first place. - The method n°3 (which is considered as another sensitivity method) performs multiple imputations (MI) for missing data, assuming a MAR missingness mechanism. As there is no other post randomization assessment of the primary endpoint when this latter is missing, the multiple imputation process must be based on baseline and post randomization covariates other than intermediate assessments of the primary endpoint. Blinded simulations have shown that important prognostic factors (such as country) could not be fitted as the model could not converge. Hence, this method based on multiple imputations relies on a somewhat subjective choice of covariates and should not be considered as the primary one.
Primary Analysis	12.10.1.2. Primary analysis “The primary model analysis will be an exact logistic regression adjusting for treatment, centre, and baseline fibrinogen (categorized into three classes, ≤ 2 g/L,]2 g/L; 4g/L], > 4 g/L)”	SAP : The primary model of analysis will be a logistic regression to assess the association between a binary exposure variable treatment (variable “_trt”) and the binary outcome (variable “_resp”), adjusting for centre and baseline fibrinogen (variable “_b_fibrinogen”,

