3.3.6.2 Primary analysis of the primary endpoint

3.3.6.2.1 Hypothesis

- Null hypothesis:

H0: the true failure rate in the Clotfact[®] randomised group = the true failure rate in the placebo group.

- Alternative hypothesis:

H1: the true failure rate in the Clotfact[®] randomised group \neq the true failure rate in the placebo group.

The nominal two-sided level of significance is set to 5%.

The primary analysis will be conducted primarily in the ITT set.

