3.3.6.2.2 Model of analysis of the primary endpoint

The primary model of analysis will be a logistic regression to assess the association between a binary exposure variable treatment (variable “_trt”) and the binary outcome (variable “_resp”), adjusting for baseline fibrinogen (variable “_b_fibrinogen”, categorized into four classes (\leq 2 g/L,]2;3] g/L,]3,4] g/L, $>$ 4 g/L) and centre (see SAS code in §7.1). Missing data will be not imputed, assuming the missing completely at random (MCAR) assumption.

The treatment effect (odds ratio of failure) with its 95% confidence interval (95% CIs) will be provided by treatment group and tested at the 5% two-sided level of significance in this model.

Validity of the primary analysis: A graphical analysis of residuals will be done for verifying that assumptions for the primary analysis are met. If adjusting for centre effects lead to convergence issues or unstable estimates, centre effect will be ignored in the analysis.

3.3.6.2.3 *Sensitivity Analyses of the primary endpoint*

3.3.6.2.3.1 Primary sensitivity analysis (MAR assumption)

Assuming the missing at random (MAR) mechanism, multiple imputation (MI) approach by Fully Conditional Specification (FCS) will be used to handle missing data of the primary efficacy endpoint.

A stepwise logistic regression will be done to identify relevant covariates by a backward elimination analysis based on iterative maximum likelihood with the Newton-Raphson algorithm using a significance level of 0.2 to retain variables in the model. Only relevant covariates will be introduced in the MI process. The number of imputations needed will be verified with relative efficiency (RE) for the fully efficient imputation (in unit of variance) and by replicating sets of imputations checking whether the estimates are stable between imputation sets. With a little of missing information (10%), only a small number of imputations are necessary.

The final set of key covariates (referenced here below in the SAS syntax as “key_covariates_for_MI”, see §7.2 for SAS code) to be accounted for in the MI model in addition to treatment and categorized baseline fibrinogen will be defined before breaking the blind.

3.3.6.2.3.2 Secondary sensitivity analysis (MNAR assumption)

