All missing data for the primary endpoint will be estimated as failures assuming a missing not at random (MNAR) mechanism. The same model as the one proposed for the primary analysis will be fitted on the new data set considering missing data as failures.

3.3.6.2.3.3 Per Protocol analyses

Same primary model analyses will also be performed in the PP set assuming the MAR, MCAR and MNAR assumptions to handle missing data of the primary efficacy endpoint.

3.3.6.2.4 *Other efficacy analyses of the primary endpoint*

- *Analysis of the baseline fibrinogen as continuous:*

A logistic model will be fitted adjusting linear and quadratic effects of baseline fibrinogen.

- *Analysis of the centre and baseline fibrinogene interactions with treatment:*

Treatment by center and treatment by categorized baseline fibrinogen interactions will be investigated in a logistic regression adjusting for baseline fibrinogen, centre and interactions (see §7.3 for SAS code).

Odds ratios with their 95%CIs will be provided by centre and treatment group and illustrated in forest plots.

3.3.6.2.5 *Individual component analyses of the primary endpoint*

The analysis of the contribution of each component of the composite primary endpoint will be considered as descriptive analyses. Odds ratios and 95%CIs will be provided.

3.3.6.2.5.1 Administration of RBCs from H0 to D2

The percentage of patients requiring the transfusion of at least 2 units of RBCs within 48 hours following IMP administration will be calculated and logistic regression adjusting for baseline fibrinogen value (categorized) will be used to compare the Clottafact[®] group and placebo group.

The same subgroup analyses planned for the primary endpoint will be performed as well.

3.3.6.2.5.2 Percentage of patients losing at least 4g/dL of haemoglobin from H0 to D2

The percentage of patients losing at least 4 g/dL of haemoglobin within 48 hours following IMP administration with regards to the haemoglobin reference level will be calculated. A logistic regression adjusting for baseline fibrinogen value (categorized) will be used to compare the Clottafact[®] group and placebo group.

The same subgroup analyses planned for the primary endpoint will be performed as well.

3.3.6.2.6 *Subset analyses*

Subset analyses will be performed to estimate the percentage of failure by treatment group and by baseline covariates level in ITT and PP sets.

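### The only MNAR analysis sets missing outcomes to failure in both arms, which is often a weak stress test: add an arm-specific tipping-point grid and align the variable names in the imputation code

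*SAP*

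**What the plan says.** **Primary analysis.** SAP 3.3.6.2.2 fits a logistic regression to the "outcome (variable “_resp”), adjusting for baseline fibrinogen" and centre. On missing outcomes it says: "Missing data will be not imputed, assuming the missing completely at random (MCAR) assumption".

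**MAR analysis.** SAP 3.3.6.2.3.1 plans multiple imputation by fully conditional specification, which "will be used to handle missing data of the primary efficacy endpoint". It points to section 7.2 for the code. There the imputation step reads "fcs logistic(resp = _trt centre _b_fibrinogen key_covariates_for_MI", and the model then fitted to each completed data set reads "model _resp = _trt centre _b_fibrinogen /influence iplots".

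**MNAR analysis.** SAP 3.3.6.2.3.2 gives one rule: "All missing data for the primary endpoint will be estimated as failures assuming a missing not at random (MNAR) mechanism". The table of changes in SAP 2.2 adds that this method "replaces missing data by failures regardless of the randomized treatment".

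SAP 3.3.6.2.3.3 repeats these approaches in the per-protocol set. Neither document plans a delta-adjusted, tipping-point, worst-case or other arm-specific analysis.

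**The concern.** The primary analysis rests on MCAR, so the argument that missing outcomes do not matter falls to the two sensitivity analyses. Each has a weakness.

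The MNAR rule treats the arms alike. A useful MNAR check asks how unfavourable to the active arm, relative to placebo, the unseen outcomes would have to be before the conclusion changes. One symmetric rule gives a single point on that scale, and the pattern of missingness decides whether the point is harsh, neutral or favourable to Clottafact. A significant result under it could be reported as robustness to MNAR when a modest difference between the arms in the unseen outcomes would remove significance.

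In the MAR code, the imputed variable is not the one analysed. In one configuration of the data set the fragment would silently reproduce the primary result, and that agreement would be read as support.

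**Working it through.** **Inputs from the documents**
- Two-sided 5% level (SAP 3.3.6.2.1); unpooled Z test, 42% v 27%, 90% power, 206 per group (protocol 12.3).
- 448 patients recruited, 1.55% assumed outside the ITT set because they received no IMP (SAP 1.11). Per arm: 448 × (1 − 0.0155) / 2 = 220.5.

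**Reproducing the plan's figure.** n = (1.960 + 1.282)² × (0.42×0.58 + 0.27×0.73) / 0.15² = 205.8, so 206 per group, as stated. The same unpooled Z test is used below. It is unadjusted, so it approximates the planned logistic model.

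**Assumptions.** Observed failure rates and missing fractions by arm are not in the documents. Two pairs of rates are used:
- 37.5% v 47.5%, a result near the significance boundary.
- 35% v 50%, the planned 15-point difference around an overall rate of 42.5%. That rate is compatible with the re-estimated 470 patients (223 per arm; 446/0.95 = 469.5), but so is 57.5%, and the SAP states neither.

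Missing fractions range from 1.55% to 8% per arm. The lower figure borrows the SAP's no-IMP rate as a convenient low value; it is not a rate of missing outcomes.

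**Formulas.** Let pA and pP be the observed failure rates, and mA and mP the missing fractions (active, placebo).
- Failure in both arms: difference = (pP − pA) + mP(1 − pP) − mA(1 − pA).
- Active=failure, placebo=success: difference = (pP − pA) − mP·pP − mA(1 − pA).

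With mA = mP = m, the first reduces to (1 − m)(pP − pA): the difference shrinks only by the missing fraction. It grows once mP/mA exceeds (1 − pA)/(1 − pP), which is 0.625/0.525 = 1.19 at 37.5% v 47.5%.

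**Worked case: 37.5% v 47.5%, 5% missing per arm**
- Complete case, 209.5 per arm: 10.0 points, SE 0.0481, z = 2.08, p = 0.037.
- Failure in both: active 0.375×0.95 + 0.05 = 0.406; placebo 0.475×0.95 + 0.05 = 0.501; 9.5 points, SE 0.0472, z = 2.01, p = 0.044.
- Active=failure, placebo=success: 0.406 v 0.475×0.95 = 0.451; 4.5 points, SE 0.0471, z = 0.96, p = 0.34.
- One step into a grid: 5% is about 11 patients per arm. With all active missing set to failure and 10 of 11 placebo missing set to failure, placebo = 0.451 + 0.05×10/11 = 0.497; 9.05 points, z = 1.92, p = 0.055.

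**Range of patterns**

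| Observed rates (active v placebo) | Missing (active / placebo) | Complete case | Failure in both | Active=failure, placebo=success |
|---|---|---|---|---|
| 37.5% v 47.5% | 5% / 5% | 10.0, p=0.037 | 9.5, p=0.044 | 4.5, p=0.34 |
| 37.5% v 47.5% | 2% / 8% | 10.0, p=0.038 | 12.95, p=0.006 | 4.95, p=0.29 |
| 37.5% v 47.5% | 8% / 2% | 10.0, p=0.037 | 6.05, p=0.20 | 4.05, p=0.39 |
| 37.5% v 47.5% | 1.55% / 1.55% | 10.0, p=0.034 | 9.8, p=0.036 | 8.3, p=0.077 |
| 35% v 50% | 5% / 5% | 15.0, p=0.0017 | 14.25, p=0.0024 | 9.25, p=0.049 |
| 35% v 50% | 1.55% / 1.55% | 15.0, p=0.0014 | 14.8, p=0.0016 | 13.2, p=0.005 |

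**The code in 7.2.** PROC MI names resp in its VAR, CLASS and FCS statements (SAS ignores case). PROC LOGISTIC models _resp, the name used in 3.3.6.2.2, 7.1, 7.3 and 7.4. The fragment also has _b_fibrinogen_ in VAR and CLASS but _b_fibrinogen in FCS and PROC LOGISTIC. If the data set holds only _resp, PROC MI stops. If it holds both outcome variables, _resp remains missing in every completed set.

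A simulation of the second situation (441 patients, 19 missing, 100 imputations) gave:
- analysing the unimputed variable: log odds ratio −0.7074, SE 0.2014, between-imputation variance zero, identical to the complete-case fit;
- analysing the imputed variable: −0.7035, SE 0.2019, between-imputation variance 0.0019.

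**The case against.** A reader might infer that the planned analyses cannot show fragility at all. The documents do not support that. Failure in both arms does bite when the active arm has more missing outcomes: at 8% v 2% it takes p from 0.037 to 0.20. With balanced missingness it still shrinks the difference slightly. Nothing in either document suggests that missingness leans towards placebo in this double-blind trial, so an illustration using only that direction would be one-sided.

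The amount missing may also be small. Protocol 5.1 notes that the endpoint is measured soon after inclusion, and SAP 3.3.3 lets haemoglobin values obtained outside the study fill gaps. With little missing and a large effect, no rule changes the conclusion. SAP 2.2 itself says that failure imputation represents one particular MNAR mechanism with strong assumptions, and for that reason keeps it out of the primary analysis. These points stand and limit the size of the concern. They do not supply an analysis that varies the assumption by arm.

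On the code, a reader might infer that the MAR analysis is invalid. That is also too strong. Section 7.2 is a fragment with placeholders for the seed and covariates, so it cannot run as printed, and the text of 3.3.6.2.3.1 correctly plans to impute the endpoint. A silent failure needs both variable names in the data set, which no document says. The planned checks are weaker protection than they seem, however. Relative efficiency and stability across replicated imputation sets both look perfect when nothing varies, and no check that the between-imputation variance exceeds zero is stated. An underscore lost in text conversion is possible but unlikely, since the short name appears three times in one block.

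**Conclusion.** The point holds as a cheap improvement to the MNAR analysis plus a near-clerical code correction. It does not show that the sensitivity strategy fails.

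The single MNAR rule is weak when missingness is balanced, favourable to Clottafact when placebo missingness is clearly higher (beyond a ratio of about 1.2 at the rates used), and a real penalty only when active missingness is higher. Whether this matters depends on two quantities that the documents do not give: the number of missing outcomes by arm and the observed effect. For a borderline result with 5% missing per arm, the planned rule would still report significance (p=0.044), although reversing its assumption in the placebo arm gives p=0.34. For the planned 15-point difference with about 1.5% missing, the conclusion survives every rule tried. All p-values come from an unadjusted Z test on assumed rates and illustrate direction and size only. Patients who received no IMP lie outside the SAP's ITT set, so neither sensitivity analysis covers them.

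**What to change.** **SAP 3.3.6.2.3.2.** Keep failure in both arms. Add a tipping-point grid: for each number of missing active outcomes set to failure (0 to all) and each number of missing placebo outcomes set to failure (0 to all), refit the primary model and report the odds ratio and p-value. Include the corner active=failure/placebo=success, mark where p crosses 0.05, and report the number of missing outcomes by arm alongside. Specify this before unblinding.

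**SAP 7.2.** Use _resp and _b_fibrinogen in every statement of PROC MI and PROC LOGISTIC, and add a check that the between-imputation variance for treatment is above zero.

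**Cost.** Corrected names, about ten lines of code and one extra table or plot. The downside for the sponsor is that the statement on robustness may turn out less favourable than under the present rule alone.

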7.3 SAS code fragments for other efficacy analyses (interactions testing)

```

ods graphics on;
ods output ParameterEstimates =_est OddsRatios =_or;
proc logistic data = Main_analysis descending;
class _trt centre _b_fibrinogen(PARAM=REF REF="> 4 g/L") / param=glm;
model _resp = _trt centre _b_fibrinogen centre*_trt centre*_b_fibrinogen
_b_fibrinogen*_trt /influence iplots;
run;
ods graphics off;

```

7.4 SAS code fragments for other efficacy analyses (subgroup analyses)

```

ods output ParameterEstimates =_est OddsRatios =_or;
proc logistic data = Main_analysis descending;
class _trt _covariate(PARAM=REF REF="covariate ref class") / param=glm;
model _resp = _trt _covariate _covariate *_trt ;
run;

```
